11.2.2 Disease Parameters

Measurable disease. Measurable lesions are defined as those that can be accurately measured in at least one dimension (longest diameter to be recorded) as ≥ 20 mm by chest x-ray or as ≥ 10 mm with CT scan, MRI, or calipers by clinical exam. All tumor measurements must be recorded in millimeters (or decimal fractions of centimeters).

Note: Tumor lesions that are situated in a previously irradiated area might or might not be considered measurable. *If the investigator thinks it appropriate to include them, the conditions under which such lesions should be considered must be defined in the protocol.*

Malignant lymph nodes. To be considered pathologically enlarged and measurable, a lymph node must be ≥ 15 mm in short axis when assessed by CT scan (CT scan slice thickness recommended to be no greater than 5 mm). At baseline and in follow-up, only the short axis will be measured and followed.

Non-measurable disease. All other lesions (or sites of disease), including small lesions (longest diameter <10 mm or pathological lymph nodes with ≥ 10 to <15 mm short axis), are considered non-measurable disease. Bone lesions, leptomeningeal disease, ascites, pleural/pericardial effusions, lymphangitis cutis/pulmonitis, inflammatory breast disease, and abdominal masses (not followed by CT or MRI), are considered as non-measurable.

Note: Cystic lesions that meet the criteria for radiographically defined simple cysts should not be considered as malignant lesions (neither measurable nor non-measurable) since they are, by definition, simple cysts.

‘Cystic lesions’ thought to represent cystic metastases can be considered as measurable lesions, if they meet the definition of measurability described above. However, if non-cystic lesions are present in the same patient, these are preferred for selection as target lesions.

Target lesions. All measurable lesions up to a maximum of 2 lesions per organ and 5 lesions in total, representative of all involved organs, should be identified as **target lesions** and recorded and measured at baseline. Target lesions should be selected on the basis of their size (lesions with the longest diameter), be representative of all involved organs, but in addition should be those that lend themselves to reproducible repeated measurements. It may be the case that, on occasion, the largest lesion does not lend itself to reproducible measurement in which circumstance the next largest lesion which can be measured reproducibly should be selected. A sum of the diameters (longest for non-nodal lesions, short axis for nodal lesions) for all target lesions will be calculated and reported as the baseline sum diameters. If lymph nodes are to be included in the sum, then only the short axis is added into the sum. The baseline sum diameters will be used as reference to further characterize any objective tumor regression in the measurable dimension of the disease.

Non-target lesions. All other lesions (or sites of disease) including any measurable lesions over and above the 5 target lesions should be identified as **non-target lesions** and should also be recorded at baseline. Measurements of these lesions are not required, but the presence, absence, or in rare cases unequivocal progression of each should be noted throughout follow-up.

11.2.3 Methods for Evaluation of Measurable Disease

All measurements should be taken and recorded in metric notation using a ruler or calipers. All baseline evaluations should be performed as closely as possible to the beginning of treatment and never more than 4 weeks before the beginning of the treatment.

The same method of assessment and the same technique should be used to characterize each identified and reported lesion at baseline and during follow-up. Imaging-based evaluation is preferred to evaluation by clinical examination unless the lesion(s) being followed cannot be imaged but are assessable by clinical exam.

Clinical lesions Clinical lesions will only be considered measurable when they are superficial (*e.g.*, skin nodules and palpable lymph nodes) and ≥ 10 mm diameter as assessed using calipers (*e.g.*, skin nodules). In the case of skin lesions, documentation by color photography, including a ruler to estimate the size of the lesion, is recommended.

Chest x-ray Lesions on chest x-ray are acceptable as measurable lesions when they are clearly defined and surrounded by aerated lung. However, CT is preferable.

Conventional CT and MRI This guideline has defined measurability of lesions on CT scan based on the assumption that CT slice thickness is 5 mm or less. If CT scans have slice thickness greater than 5 mm, the minimum size for a measurable lesion should be twice the slice thickness. MRI is also acceptable in certain situations (*e.g.* for body scans).

Use of MRI remains a complex issue. MRI has excellent contrast, spatial, and temporal resolution; however, there are many image acquisition variables involved in MRI, which greatly impact image quality, lesion conspicuity, and measurement. Furthermore, the availability of MRI is variable globally. As with CT, if an MRI is performed, the technical specifications of the scanning sequences used should be optimized for the evaluation of the type and site of disease. Furthermore, as with CT, the modality used at follow-up should be the same as was used at baseline and the lesions should be measured/assessed on the same pulse sequence. It is beyond the scope of the RECIST guidelines to prescribe specific MRI pulse sequence parameters for all scanners, body parts, and diseases. Ideally, the same type of scanner should be used and the image acquisition protocol should be followed as closely as possible to prior scans. Body scans should be performed with breath-hold scanning techniques, if possible.

PET-CT At present, the low dose or attenuation correction CT portion of a combined PET-CT is not always of optimal diagnostic CT quality for use with RECIST measurements. However, if the site can document that the CT performed as part of a PET-CT is of identical diagnostic quality to a diagnostic CT (with IV and oral contrast), then the CT portion of the PET-CT can be used for RECIST measurements and can be used interchangeably with conventional CT in accurately measuring cancer lesions over time.

Note, however, that the PET portion of the CT introduces additional data which may bias an investigator if it is not routinely or serially performed.

Ultrasound Ultrasound is not useful in assessment of lesion size and should not be used as a method of measurement. Ultrasound examinations cannot be reproduced in their entirety for independent review at a later date and, because they are operator dependent, it cannot be guaranteed that the same technique and measurements will be taken from one assessment to the next. If new lesions are identified by ultrasound in the course of the study, confirmation by CT or MRI is advised. If there is concern about radiation exposure at CT, MRI may be used instead of CT in selected instances.

Endoscopy, Laparoscopy The utilization of these techniques for objective tumor evaluation is not advised. However, such techniques may be useful to confirm complete pathological response when biopsies are obtained or to determine relapse in trials where recurrence following complete response (CR) or surgical resection is an endpoint.

Tumor markers Tumor markers alone cannot be used to assess response. If markers are initially above the upper normal limit, they must normalize for a patient to be considered in complete clinical response. Specific guidelines for both CA-125 response (in recurrent ovarian cancer) and PSA response (in recurrent prostate cancer) have been published [*JNCI* 96:487-488, 2004; *J Clin Oncol* 17, 3461-3467, 1999; *J Clin Oncol* 26:1148-1159, 2008]. In addition, the Gynecologic Cancer Intergroup has developed CA-125 progression criteria which are to be integrated with objective tumor assessment for use in first-line trials in ovarian cancer [*JNCI* 92:1534-1535, 2000].

Cytology, Histology These techniques can be used to differentiate between partial responses (PR) and complete responses (CR) in rare cases (e.g., residual lesions in tumor types, such as germ cell tumors, where known residual benign tumors can remain).

The cytological confirmation of the neoplastic origin of any effusion that appears or worsens during treatment when the measurable tumor has met criteria for response or stable disease is mandatory to differentiate between response or stable disease (an effusion may be a side effect of the treatment) and progressive disease.

FDG-PET While FDG-PET response assessments need additional study, it is sometimes reasonable to incorporate the use of FDG-PET scanning to complement CT scanning in assessment of progression (particularly possible 'new' disease). New lesions on the basis of FDG-PET imaging can be identified according to the following algorithm:

- a. Negative FDG-PET at baseline, with a positive FDG-PET at follow-up is a sign of PD based on a new lesion.
- b. No FDG-PET at baseline and a positive FDG-PET at follow-up: If the positive FDG-PET at follow-up corresponds to a new site of disease confirmed by CT, this is PD. If the positive FDG-PET at follow-up is not confirmed as a new site of disease on CT, additional follow-up CT scans are needed to determine if there is truly progression occurring at that site (if so, the date of PD will be the date of the initial abnormal FDG-PET scan). If the positive FDG-PET at follow-up corresponds to a pre-existing site of disease on CT that is not progressing on the basis of the anatomic images, this is not PD.
- c. FDG-PET may be used to upgrade a response to a CR in a manner similar to a biopsy in cases where a residual radiographic abnormality is thought to represent fibrosis or

scarring. The use of FDG-PET in this circumstance should be prospectively described in the protocol and supported by disease-specific medical literature for the indication. However, it must be acknowledged that both approaches may lead to false positive CR due to limitations of FDG-PET and biopsy resolution/sensitivity.

Note: A ‘positive’ FDG-PET scan lesion means one which is FDG avid with an uptake greater than twice that of the surrounding tissue on the attenuation corrected image.

11.2.4 Response Criteria

11.2.4.1 Evaluation of Target Lesions

Complete Response (CR): Disappearance of all target lesions. Any pathological lymph nodes (whether target or non-target) must have reduction in short axis to <10 mm.

Partial Response (PR): At least a 30% decrease in the sum of the diameters of target lesions, taking as reference the baseline sum diameters.

Progressive Disease (PD): At least a 20% increase in the sum of the diameters of target lesions, taking as reference the smallest sum on study (this includes the baseline sum if that is the smallest on study). In addition to the relative increase of 20%, the sum must also demonstrate an absolute increase of at least 5 mm. (Note: the appearance of one or more new lesions is also considered progressions).

Stable Disease (SD): Neither sufficient shrinkage to qualify for PR nor sufficient increase to qualify for PD, taking as reference the smallest sum diameters while on study.

11.2.4.2 Evaluation of Non-Target Lesions

Complete Response (CR): Disappearance of all non-target lesions and normalization of tumor marker level. All lymph nodes must be non-pathological in size (<10 mm short axis).

Note: If tumor markers are initially above the upper normal limit, they must normalize for a patient to be considered in complete clinical response.

Non-CR/Non-PD: Persistence of one or more non-target lesion(s) and/or maintenance of tumor marker level above the normal limits.

Progressive Disease (PD): Appearance of one or more new lesions and/or *unequivocal progression* of existing non-target lesions. *Unequivocal progression* should not normally trump target lesion status. It must be representative of overall disease status change, not a single lesion increase.

Although a clear progression of “non-target” lesions only is exceptional, the opinion of the treating physician should prevail in such circumstances, and the progression status should be confirmed at a later time by the review panel (or Principal Investigator).

11.2.4.3 Evaluation of Best Overall Response

The best overall response is the best response recorded from the start of the treatment until disease progression/recurrence (taking as reference for progressive disease the smallest measurements recorded since the treatment started). The patient's best response assignment will depend on the achievement of both measurement and confirmation criteria.

For Patients with Measurable Disease (*i.e.*, Target Disease)

Target Lesions	Non-Target Lesions	New Lesions	Overall Response	Best Overall Response when Confirmation is Required*
CR	CR	No	CR	≥4 wks. Confirmation**
CR	Non-CR/Non-PD	No	PR	≥4 wks. Confirmation**
CR	Not evaluated	No	PR	
PR	Non-CR/Non-PD/not evaluated	No	PR	Documented at least once ≥4 wks. from baseline**
SD	Non-CR/Non-PD/not evaluated	No	SD	
PD	Any	Yes or No	PD	no prior SD, PR or CR
Any	PD***	Yes or No	PD	
Any	Any	Yes	PD	

* See RECIST 1.1 manuscript for further details on what is evidence of a new lesion.
 ** Only for non-randomized trials with response as primary endpoint.
 *** In exceptional circumstances, unequivocal progression in non-target lesions may be accepted as disease progression.

Note: Patients with a global deterioration of health status requiring discontinuation of treatment without objective evidence of disease progression at that time should be reported as “*symptomatic deterioration*.” Every effort should be made to document the objective progression even after discontinuation of treatment.

For Patients with Non-Measurable Disease (*i.e.*, Non-Target Disease)

Non-Target Lesions	New Lesions	Overall Response
CR	No	CR
Non-CR/non-PD	No	Non-CR/non-PD*
Not all evaluated	No	not evaluated
Unequivocal PD	Yes or No	PD
Any	Yes	PD

* ‘Non-CR/non-PD’ is preferred over ‘stable disease’ for non-target disease since SD is increasingly used as an endpoint for assessment of efficacy in some trials so to assign this category when no lesions can be measured is not advised

11.2.5 Duration of Response

Duration of overall response: The duration of overall response is measured from the time measurement criteria are met for CR or PR (whichever is first recorded) until the first date that recurrent or progressive disease is objectively documented (taking as reference for progressive disease the smallest measurements recorded since the treatment started).

The duration of overall CR is measured from the time measurement criteria are first met for CR until the first date that progressive disease is objectively documented.

Duration of stable disease: Stable disease is measured from the start of the treatment until the criteria for progression are met, taking as reference the smallest measurements recorded since the treatment started, including the baseline measurements.

11.2.6 Progression-Free Survival

Progression-free survival (PFS) is defined as the duration of time from start of treatment to time of progression or death, whichever occurs first.

12. DATA REPORTING / REGULATORY REQUIREMENTS

Adverse event lists, guidelines, and instructions for AE reporting can be found in Section 7.0 (Adverse Events: List and Reporting Requirements).

12.1.1 Method

This study will be monitored by the Markey Cancer Center Data and Safety Monitoring Committee. Adverse event and quality assessment will be submitted to DSMC using electronic case report form in OnCore.

12.1.2 Responsibility for Data Submission

Study CRA's and investigators are responsible for submitting data and/or data forms to OnCore. The date for submission to OnCore will be set by the CRDM SRF. The OnCore Management staff is responsible for compiling and submitting study data to DSMC for all participants and for providing the data to the Principal Investigator for review.

13. STATISTICAL CONSIDERATIONS

13.1 Study Design/Endpoints

This non-randomized, pilot study plans to enroll 35 total patients with previously untreated squamous cell cancer of the head and neck. As the goal of this study is to obtain preliminary data regarding current standard therapy compliance rates for this patient population at the University of Kentucky Markey Cancer Center and assess feasibility of an additional beet juice supplementation during therapy, the primary objective is to estimate treatment compliance defined as completion of radiation alone or radiation and chemotherapy with beet root supplementation during primary treatment. Treatment compliance is defined in more detail in section 5. Secondary objectives to obtain pilot estimates for cancer specific outcomes such as response rate, adverse events, mucositis rates, and 1 and 2 year locoregional control rates and progression-free rates Additional secondary

measures will include strength measures, CT scans, quality of life surveys, nitrate/nitrite levels, endurance testing, handgrip strength, and Body Composition DXA variables of interest (Bone Mineral Density, Bone Mineral Content, Area, % fat). Beet juice rates of completion will also be estimated to assess feasibility of this product.

13.2 Sample Size/Accrual Rate

The primary endpoint of this study is treatment compliance, for the chemoradiation strata defined as completion of radiotherapy and 3 cycles of chemotherapy with no treatment delay with published historical rates average around 52.1% (30). For those receiving radiation alone, we predict higher compliance rates closer to 70% as these patients tend to experience less mucositis and adverse events during treatment. We anticipate 60% of patients will receive radiation alone versus 40% receiving chemoradiation. 25 total patients (10 – chemoradiation, 15 – radiation alone) receiving beet root supplementation, will result in 90% confidence intervals around each estimated compliance rate with a maximum widths of +/- 27.75% and 22.85% for chemoradiation and radiation alone respectively. The combined estimate of compliance will still have a 90% confidence interval estimate with a maximum width of +/- 17.7% as previously designed. For the 10 subjects in the observational cohort not receiving beet root supplementation, we will still be able to estimate compliance rates +/- 27.75% and obtain pilot data regarding strength outcomes during standard of care therapy. This design is not powered to compare compliance rates between treatment strata or beet root versus standard of care; instead it allows us to gain preliminary information about these rates with a certain amount of precision as pilot data for a larger, more definitive study. We plan to accrue patients over a 2 year period.

There will be a pre-specified safety consideration after half of the planned enrollment in the beet root supplementation (interim after 13) to verify acceptable treatment completion rates as compared to a published historical rate of 52.1%. Two prior beta distributions (non-informative and null-hypothesis based) will be considered with patient information collected from the first 13 enrolled in beet root arm to calculate the posterior probability that the mean proportion of successful completion is less than or equal to historical rates of 52.17% with corresponding 90% credible intervals. The study team will reconsider continuation of the protocol due to safety and feasibility concerns if either arm has a high probability of experiencing a success rate lower than published rates.

13.3 Data Analysis

Following study completion, primary data analysis will include estimation of subjects achieving treatment compliance along with corresponding exact 90% binomial confidence intervals.

Other secondary endpoints listed in section 13.1 will be primarily descriptive as they are exploratory in nature; however means and standard deviations (or N and percentages where appropriate) will be estimated and summarized for each time point to gain more information of expected effect size differences between standard therapy and BR arms. Repeated measures ANOVA will be utilized to test for exploratory differences in these various measures over time points between BR and standard therapy arms. Kaplan-Meier curves will be presented for locoregional control and progression-free survival along with 90% confidence interval bounds. Exploratory log rank tests will be performed to assess for any preliminary differences in these survival outcomes by treatment arm.

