1.2 Secondary Objectives

- Quantify changes in strength, and body composition, before and following supplementation
- Determine feasibility of beetroot supplementation in head and neck cancer patients defined for each patient as the proportion of days successfully consumed supplement during treatment schedule
- Determine the toxicity of concentrated beetroot given in conjunction with radiation or chemo-radiation in SCCHN as measured by CTCAE v. 4.0
- Evaluate the trend in grade of mucositis during radiotherapy or chemoradiotherapy as measured weekly by CTCAE v 4.0
- Determine 1- and 2-year locoregional control rate and progression-free survival of subjects enrolled on this clinical trial.

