5. TREATMENT PLAN

This is a non-randomized, pilot Phase II clinical trial that will determine the safety of concentrated beet root given in conjunction with radiation or radiation plus chemotherapy for locally advanced head and neck cancer. This trial will enroll 25 subjects taking beetroot supplement with up to an additional 10 standard of care subjects that refuse participation in the beetroot supplementation but are willing to obtain strength outcomes during their cancer treatment for a maximum of 35 patients.

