5.1.5 Testing procedures at Baseline, Midpoint and Endpoint of therapy

All testing procedures, unless otherwise indicated, will be performed at the Markey Cancer Center (MCC) and the Center for Clinical and Translational Science (CCTS). Testing will occur at Baseline (Pre-IMRT), Midpoint (week number 7-8 following IMRT initiation), and Endpoint (4-6 weeks following Midpoint testing). A range of testing times at midpoint and endpoint are provided for subject convenience and flexibility with medical follow-up appointments. Primary outcome measure: 1) IMRT treatment compliance- No delays in treatment of radiation and/or chemotherapy (Cycles: Namely 35 fraction of daily radiation therapy (Monday-Friday) with 100 mg/m² cisplatin on days 1, 21, & 43. Total duration of therapy = 50 days). Treatment compliance will be defined as completion of all radiotherapy or completion of all radiotherapy plus prescribed chemotherapy without dose reduction or delay of radiation therapy that would extend treatment beyond 50 days.; Secondary outcome measures: 1) muscle strength/function, 2) serum/salivary nitrate/nitrite, 3) preservation of fat-free mass (CT/DXA), 4) mucositis symptoms, 5) nutrition assessment, 6) quality of life g. Details of each test are provided in section 9.0.

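### Change in strength and body composition is the first secondary objective, but section 13.3 plans no within-patient change, SD of change, correlation or interval

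*Combined protocol and SAP*

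**What the plan says.** The first secondary objective in section 1.2 is: "Quantify changes in strength, and body composition, before and following supplementation". Section 5.1.5 sets three test occasions for each patient, and the calendars in 10.2 and 10.3 place strength testing, DXA and body-composition CT at all three in both cohorts. On numbers, section 5 states: "This trial will enroll 25 subjects taking beetroot supplement with up to an additional 10 standard of care subjects". The second group consists of patients who decline the supplement, so the cohorts are not randomized.

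For the secondary measures, section 13.3 plans two things. The first is descriptive: means and SDs, or counts and percentages, "will be estimated and summarized for each time point to gain more information of expected effect size differences between standard therapy and BR arms". The second is a test: "Repeated measures ANOVA will be utilized to test for exploratory differences in these various measures over time points between BR and standard therapy arms".

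Sections 13.1 to 13.4 name no change from baseline, SD of change, within-patient correlation, number of paired patients or interval for change. Section 13.3 does specify exact 90% intervals for compliance and 90% bounds for the Kaplan-Meier curves.

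**The concern.** The objective is about change within patients, whereas the planned summary describes each visit separately. Three things follow.

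- A visit SD measures spread between patients at one time. The SD of change also depends on how strongly a patient's visits are correlated, and that correlation is not among the planned outputs. Anyone using the pilot tables to size a later trial on change would have to guess it.
- Visit means are taken over whoever was tested. Section 5.3 removes patients who complete less than half of planned therapy, or who have intercurrent illness, unacceptable adverse events or withdraw. If weaker patients are lost more often, a shift in the visit mean mixes change with selection. Sections 13.3 and 13.4 give no rule for missed visits in these measures.
- The ANOVA is specified as a comparison between arms. It is not specified as an estimate, with an interval, of change in the 25 supplemented patients.

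At stake is whether the first secondary objective gets a direct answer, and whether the effect-size information that 13.3 says it seeks can be used by the next study's designers.

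**Working it through.** **Inputs.** From the documents: three visits per patient (5.1.5), 25 supplemented and up to 10 observational patients (5), and visit means and SDs as the source of effect-size information (13.3). Assumed, because the documents give no value: r, equal SDs at each visit, and, for the sample-size illustration, an arm difference of 0.5 visit SD, two-sided alpha 0.05, 80% power and 1:1 allocation.

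**The plan's own figures.** The only precision figures in 13.2 concern compliance. The maximum half-width of the exact (Clopper-Pearson) 90% interval is 27.76% for n = 10, 22.81% for n = 15 and 17.67% for n = 25, against 27.75%, 22.85% and 17.7% stated. These reproduce to within rounding. No effect size, SD, correlation or power is stated for strength or body composition, so there is nothing further to reproduce.

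**Step 1: from visit SD to SD of change.** With equal visit SDs, Var(change) = SD² + SD² - 2r·SD², so SD of change / visit SD = sqrt(2(1-r)). A two-arm comparison of means needs n per arm proportional to the variance: 63 using the visit SD, and about 63 × 2(1-r) using the SD of change.

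| Assumed r | SD of change / visit SD | n per arm, SD of change | n per arm, visit SD |
|---|---|---|---|
| 0.3 | 1.18 | 88 | 63 |
| 0.5 | 1.00 | 63 | 63 |
| 0.7 | 0.77 | 38 | 63 |
| 0.8 | 0.63 | 26 | 63 |
| 0.9 | 0.45 | 13 | 63 |

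The direction of the error reverses at r = 0.5.

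**Step 2: what the ANOVA can recover.** Its within-patient mean square estimates the average variance minus the average covariance over the three pairs of visits, so sqrt(2 × MS within) is a pooled SD of change. Simulation (4,000 runs, 25 + 10 patients, three visits, visit SD = 1) gave:

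- Equal correlations: 0.629 against a true 0.632 (r = 0.8), and 0.447 against 0.447 (r = 0.9).
- Correlation decaying with time (0.8 between adjacent visits, 0.8² = 0.64 from baseline to endpoint): one value, 0.71. The true values are sqrt(2 × 0.20) = 0.63 to midpoint and sqrt(2 × 0.36) = 0.85 to endpoint.

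In the second case the expected pooled variance is 2 × [1 - (0.8 + 0.8 + 0.64)/3] = 0.507. A baseline-to-endpoint trial sized on it would have 0.507/0.72 = 70% of the patients needed. A baseline-to-midpoint trial would have 0.507/0.40 = 127%.

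**Step 3: visit means.** If the same patients attend both visits, the difference of visit means equals the mean change. If a fraction f, whose mean is D below that of the others, misses the later visit, the visit mean rises by f × D with nobody stronger. As an invented illustration, 5 of 25 patients lying 10 kg below the rest on grip give (5/25) × 10 = 2 kg. The documents supply neither f nor D.

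**The case against.** Much can be said for the plan. The main goals in 13.1 are compliance and feasibility, 13.2 sizes the study on compliance, and 13.3 calls the secondary endpoints mainly descriptive. Section 13.5 stores the strength, CT, DXA and quality-of-life data under one sequence number per subject, so change can be computed later from existing records. Repeated measures ANOVA is a within-patient method that removes stable between-patient variation. Mean change follows from the visit means in patients who attend both visits. The visit SD is also useful in its own right: a baseline-adjusted design needs it together with r.

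All of this stands, and it rules out three stronger readings that a reader might infer. One is that the pilot cannot yield an effect size: it can, from data it already collects. Another is that effect size is what the pilot is run for: 13.1 and 13.2 say otherwise. The third is that a later trial sized on the visit SD would be several times too large: that needs r of 0.8 or more, and at r = 0.3 such a trial would be too small. With roughly seven weeks of radiotherapy and a further 4-6 weeks between first and last tests, in a mix of radiation-alone and chemoradiation patients, a high r cannot be taken for granted.

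The objection does not close the gap. The plan does not say that the ANOVA error term will be reported or used for an SD of change. That term gives only one pooled value for two different intervals, and no estimate or interval for change in either cohort is specified.

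**Conclusion.** The point holds as a mismatch between objective and planned output. Section 1.2 asks for change; 13.3 specifies visit summaries and a between-arm test, and takes its effect-size information from the visit summaries. Those summaries leave the SD of change undetermined, between 1.18 and 0.45 times the visit SD over assumed r of 0.3 to 0.9. Under the stated sample-size assumptions that corresponds to 88 down to 13 per arm, against 63 from the visit SD. The range shows what is lost by not reporting r; it does not predict the error in any particular trial.

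The size is modest. The endpoints are secondary and exploratory in a non-randomized pilot, and the compliance analysis, the safety analysis and the interim look do not depend on them. The change is still worth making, because it answers the first secondary objective directly at almost no cost.

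**What to change.** In section 13.3, for each strength, CT and DXA measure, add by cohort:

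- within-patient change, midpoint minus baseline and endpoint minus baseline, with number of pairs, mean, SD and 90% CI;
- the correlation between the visits in each pair.

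Keep the visit means and SDs, and base effect-size information for the next study on both sets. Keep the ANOVA as the exploratory between-arm test.

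State that the paired estimates apply to patients with both visits. They stop the mean shifting merely because attendance changed, but do not by themselves remove bias if dropout is related to outcome. Report baseline values of patients who miss the midpoint or endpoint so that readers can judge this. With 25 and up to 10 patients, the SDs and correlations will be imprecise and should be described so.

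Cost: a few table columns and a short listing. No new visits, measurements or patients.
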